6.1.7.2 Discontinuation from subsequent 3BNC117/10-1074 infusions

Participants will be discontinued from second or third 3BNC117/10-1074 infusions for any of the following reasons:

- 1. A disease or condition or an adverse event that may develop, regardless of relationship to 3BNC117 or 10-1074, if the principal investigator or designee is of the opinion that other 3BNC117 or 10-1074 infusions will jeopardize the safety of the participant.
- 2. Any immediate hypersensitivity reaction (such as urticarial rash; bronchospasm; laryngeal edema; anaphylaxis; syncope).
- 3. Any grade 2 ophthalmologic adverse event deemed related to the study products, or any grade 3 or 4 ophthalmologic adverse event regardless of causality assessment.
- 4. Any ALT or AST increase equal to or greater than 3x the upper limit of normal with concurrent increase in total bilirubin equal to or greater than 2x the upper limit of normal. Additionally, such an occurrence will also result in a consultation with a hepatologist to assess for other evidence of drug toxicity.
- 5. Any participant with a graded elevation in total bilirubin will undergo a diagnostic workup at no cost to the participant that includes right upper quadrant ultrasound, testing for gamma glutamyl transferase (GGT), HAV, HBV, HCV, EBV serologies, CMV serologies, VZV serologies, HSV serologies, and any other relevant laboratory tests as determined by the investigators. Further administration of the investigational products will be discontinued for any participant with a grade 3 or above elevation in total bilirubin for whom this evaluation fails to determine the etiology.
- 6. Life threatening medical event following 3BNC117 and/or 10-1074 unless not related to the investigational product.
- 7. Intercurrent use of immunosuppressive medication considered significant by the trial physician (e.g., systemic corticosteroids).
- 8. Pregnancy.
- 9. Participant's request to discontinue further 3BNC117 or 10-1074 infusions.

- 10. A participant in Groups 2 or 3 who misses the second dose of mAbs or placebo will not receive the third dose.
- 11. Any participant who misses an infusion will not attend the Day +2 visit following the missed dose.

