6.2.2 Randomization

This study is randomized and double-blinded. Randomized treatment assignments will be generated by the Rockefeller University Hospital pharmacy. The 8 participants in each group will be randomized in a ratio of 6 study drug recipients to 2 placebo recipients. Randomization will be generated using SAS 9.4. Blinding will not apply to the assignment of dose levels (3 or 10 mg/kg). The study preparation will be provided to the study nurses for injection under a coded, masked identification. The placebo and mAb preparations will be indistinguishable in the preparation provided for participants. The nurses, study staff, investigators, and participants will be blinded as to the identity of the study preparation. Participants will be unblinded at the end of the study. To accomplish this, study nurses will be provided with the randomization code after the study has been completed, and they will notify each participant. In the event of a medical emergency wherein knowledge of the treatment assignment will influence the participant's care, the Principal Investigator may unblind the treatment assignment.

6.2.3 3BNC117 and 10-1074 Administration Procedure

3BNC117 is provided in single-use vials containing 5 ml of the product at a concentration of 20 mg/ml. The volume of 3BNC117 to be administered will be calculated by the site research pharmacist, according to study assignment. The appropriate volume of 3BNC117 will be diluted in sterile normal saline to a total volume of 100 ml, and will be administered as an intravenous infusion over 60 minutes.

10-1074 will be provided in single-use vials containing 5 ml of the product at a concentration of 20 mg/ml. The volume of 10-1074 to be administered will be calculated by the RUH research pharmacist, according to study assignment. The appropriate volume of 10-1074 will be diluted in sterile normal saline to a total volume of 100 ml and will be administered as a slow intravenous infusion over 60 minutes.

- Sterile saline, NaCl 0.9% (placebo) will be dispensed in a volume of 100 ml, and will be administered as a slow intravenous infusion over 60 minutes. A second bag of sterile saline will be administered after the infusion of the first saline bag is completed and the line is flushed.

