1. If > 1 grade 3 or higher adverse events deemed probably or definitely related to the study drugs occur in a single group, no additional administration of the investigational product will take place pending a Safety Monitoring Committee (SMC) review. The SMC will provide a recommendation regarding subsequent enrollment in the study.

2. If there is one SAE judged as possibly, probably or definitely related to the administration of 3BNC117 and/or 10-1074 by the principal investigator or designee, no additional administration of the investigational product will take place pending a review by at least two members of the SMC. Following this review, the SMC will make a recommendation to the principal investigator regarding the continuation of investigational product administration.

SAEs, which are deemed possibly, probably or definitely related to 3BNC117 and/or 10-1074 by the principal investigator or designee, and unanticipated adverse events will be reported to the SMC within 2 working days of the site becoming aware of the event.

3. If, at any time, a fatal, life-threatening or permanently disabling SAE with a suspected causal relationship to 3BNC117 and/or 10-1074 occurs, no further administration of the

investigational products will occur until a consensus plan forward has been approved by investigators, SMC, the IRB, and the FDA.

4. The SMC will be informed within 2 working days of any participant who discontinues study treatments as a result of a grade 2 ophthalmologic adverse event deemed related to the study products or a grade 3 or 4 ophthalmologic adverse event deemed unrelated to the study drugs.

5. The SMC will be informed within 2 working days of any participant who discontinues receipt of the study products as a result of liver test abnormalities as described in Section 6.1.7.2.

6. In addition, the SMC will be asked to review on an interim basis:

- Severe solicited and unsolicited adverse events judged by the principal investigator or designee to be possibly, probably or definitely related to 3BNC117 and/or 10-1074.

- Severe laboratory adverse events confirmed on retest and judged by the principal investigator or designee to be possibly, probably or definitely related to 3BNC117 and/or 10-1074.

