13.4 Reporting Adverse Events

All adverse events will be reported to the IRB and the SMC at least annually. Serious Adverse Events, (SAEs) will be reported to the IRB and the SMC, within two working days of identification of the SAE. SAEs will be reported directly to the FDA, per 21 CFR 312.

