13.5 Reporting Unanticipated AEs

Unanticipated Adverse Events (UAEs) will be reported to the IRB and SMC. UAEs that are related and greater than moderate severity must be reported to the IRB and SMC, within two working days of identification of the UAE. UAEs will be reported to the FDA, per 21 CRF 312.

13.6 Clinical Laboratory Improvement Amendment/Clinical Laboratory Evaluation Program (CLIA/CLEP)

This study includes tests that are not CLIA/CLEP certified. The results of such tests will not be used in clinical decision-making or shared with participants or their health care providers.

14 Clinical Trial Registration

The proposed study involves testing of FDA regulated drugs or biologics and will be registered at www.ClinicalTrials.gov.

15 Bibliography

- Armbruster, C., G. M. Stiegler, B. A. Vcelar, W. Jager, U. Koller, R. Jilch, C. G. Ammann, M. Pruenster, H. Stoiber and H. W. Katinger (2004). "Passive immunization with the anti-HIV-1 human monoclonal antibody (hMAb) 4E10 and the hMAb combination 4E10/2F5/2G12." J Antimicrob Chemother 54(5): 915-920.
- Baeten, J. M., D. Donnell, P. Ndase, N. R. Mugo, J. D. Campbell, J. Wangisi, J. W. Tappero, E. A. Bukusi, C. R. Cohen, E. Katabira, A. Ronald, E. Tumwesigye, E. Were, K. H. Fife, J. Kiarie, C. Farquhar, G. John-Stewart, A. Kakia, J. Odoyo, A. Mucunguzi, E. Nakku-Joloba, R. Twesigye, K. Ngure, C. Apaka, H. Tamooh, F. Gabona, A. Mujugira, D. Panteleeff, K. K. Thomas, L. Kidoguchi, M. Krows, J. Revall, S. Morrison, H. Haugen, M. Emmanuel-Ogier, L. Ondrejcek, R. W. Coombs, L. Frenkel, C. Hendrix, N. N. Bumpus, D. Bangsberg, J. E. Haberer, W. S. Stevens, J. R. Lingappa and C. Celum (2012). "Antiretroviral prophylaxis for HIV prevention in heterosexual men and women." N. Engl. J. Med. 367(5): 399-410.
- Caskey, M., F. Klein, J. C. C. Lorenzi, M. S. Seaman, A. P. West Jr., N. Buckley, G. Kremer, L. Nogueira, M. Braunschweig, J. F. Scheid, J. A. Horwitz, I. Shimeliovich, S. Ben-Avraham, M. Witmer-Pack, M. Platten, C. Lehmann, L. A. Burke, T. Hawthorne, R. J. Gorelick, B. D. Walker, T. Keler, R. M. Gulick, G. Fatkenheuer, S. J. Schlesinger and M. C. Nussenzweig (2015). "Viraemia suppressed in HIV-1-infected humans by broadly neutralizing anitbody 3BNC117." Nature 522:487-489.
- Cohen, M. S. and L. R. Baden (2012). "Preexposure prophylaxis for HIV--where do we go from here?" N. Engl. J. Med. **367**(5): 459-461.

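### The SMC notice rule for eye events (13.1 item 4) says unrelated where the stopping rule (6.1.7.2 item 3) covers any causality, so one class of related grade 3-4 eye event has no notice deadline

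*Protocol*

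**What the plan says.** Section 6.1.7.2 item 3 lists the eye events that end further dosing: a grade 2 event deemed related to the products, or "any grade 3 or 4 ophthalmologic adverse event regardless of causality assessment".

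Section 13.1 item 4 requires that the SMC hear within 2 working days of a participant who stops treatment for an eye event. It names two kinds: a related grade 2 event, and "a grade 3 or 4 ophthalmologic adverse event deemed unrelated to the study drugs".

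Section 13.1 item 5 sets the same deadline for participants who stop "as a result of liver test abnormalities as described in Section 6.1.7.2". It refers back to the stopping rule and adds no causality condition.

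Other clauses also bring events to the SMC:

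- The text under 13.1 item 2 covers related serious events "and unanticipated adverse events will be reported to the SMC within 2 working days of the site becoming aware of the event".
- Section 13.4: "Serious Adverse Events, (SAEs) will be reported to the IRB and the SMC, within two working days of identification of the SAE".
- Section 13.5: "UAEs that are related and greater than moderate severity must be reported to the IRB and SMC, within two working days".
- Section 13.1 item 6 covers severe events judged possibly, probably or definitely related. It opens "In addition, the SMC will be asked to review on an interim basis" and gives no time limit.

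**The concern.** Item 4 is meant to tell the SMC about participants taken off treatment under the eye rule, but its list does not match that rule. Of the three kinds of eye event that stop dosing, it names two and omits the related grade 3-4 event, which is the most informative about the product. On the wording of item 4 alone, a related eye event has a 2-working-day deadline at grade 2 and loses it at grade 3.

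Eye safety is a named concern in this trial. Section 12 reports that 3BNC117 stained cells in the conjunctival recesses and 10-1074 stained optic-nerve cells in human tissue, and that 12 of 68 recipients of 3BNC117 had mild eye complaints. It also states that the two antibodies have not been given together before. If a related severe eye event reached the SMC late, other participants could receive further infusions in the meantime. What is at stake is the timing of oversight. The affected participant stops dosing whatever the cause.

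**Working it through.** No sample size, power or error rate bears on this, so the check is a comparison of clauses followed by a count of where item 4 can apply.

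**Step 1. Stopping rule against notice rule**

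| Eye event | Stops dosing (6.1.7.2 item 3) | 2-working-day notice under 13.1 item 4 |
|---|---|---|
| Grade 2, related | Yes | Yes |
| Grade 3-4, unrelated | Yes | Yes |
| Grade 3-4, related | Yes | No |

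**Step 2. Other routes to the SMC for a single related grade 3-4 eye event that is neither serious nor classed as unanticipated**

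| Clause | Does it set a deadline for this event? |
|---|---|
| 13.1 item 1 | No. It needs more than one grade 3 or higher event in a group, each probably or definitely related. |
| 13.1 items 2 and 3 | No. Serious events only. |
| 13.1, text under item 2 | No. Related serious or unanticipated events only. |
| 13.1 item 5 | No. Liver tests only. |
| 13.1 item 6 | The event is covered, but no time limit is given and there is no automatic pause. |
| 13.4 | The 2-day limit is for serious events. Otherwise reporting is at least annual. |
| 13.5 | No. The 2-day limit is for unanticipated events. |
| 6.1.7.4 | No. It applies on withdrawal from the study and states no deadline. |
| 12.1 | No. The SMC is available for consultation if needed. |

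No clause gives this event a deadline. If the same event is serious or unanticipated, the 2-working-day limit applies.

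**Step 3. Where item 4 can apply**

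Item 4 depends on a participant discontinuing treatment, so doses must remain.

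- Group 1 has one infusion (section 7.1), so 0 participants.
- Groups 2 and 3 have 6 active and 2 placebo participants each (section 6.2.2): 2 × (6 + 2) = 16. Placebo recipients count because relatedness is judged blind: "The nurses, study staff, investigators, and participants will be blinded as to the identity of the study preparation".
- The last infusion is at Week 16 and follow-up lasts 24 weeks after it: 16 + 24 = 40 weeks in the study.
- The window is Weeks 0 to 16: 16 / 40 = 40% of that time.
- The scheduled eye exam in Groups 2 and 3 is at Week 20 (section 6.1.4), 20 − 16 = 4 weeks after the window closes. An event first found there does not trigger item 4, whatever its cause.

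These figures bound where item 4 operates. They say nothing about how often the omitted event would occur, and no event risk is assumed.

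**The case against.** The strongest reply is that item 4 complements item 6 by design. Item 6 already sends every severe related event to the SMC. The eye discontinuations it does not reach are the related grade 2 and the unrelated grade 3-4 events, which are exactly the two that item 4 lists. On that reading every eye discontinuation has a route to the SMC. This part stands: the event is not hidden from the committee. It does not answer the point about timing, because item 6 has no deadline and item 4 does.

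A second reply is that the residual case may be empty. Section 12 describes only mild eye complaints, and section 3.3.4 reports no grade 3 or 4 event deemed related to 3BNC117 in its phase 1 study. A related severe eye event could therefore well be classed as unanticipated, and section 13.5 would then require notice in 2 working days. This is fair, and if every such event were so classed only the wording mismatch would remain. But the text shown does not define unanticipated. The protocol itself names the eye as a site of possible risk and writes grade 3-4 eye events into its stopping rule, so a site could reasonably call one anticipated. The deadline should not rest on that judgement.

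It is also true that the protocol as a whole treats related events more strictly: a related serious event, or more than one probably or definitely related grade 3 or higher event in a group, pauses dosing. The reversed order of notice is confined to the residual case. The 16 participants and the 40% window do not measure how often that case would arise.

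**Conclusion.** The concern holds as a minor inconsistency in a safety-notification rule. A grade 3-4 eye event that stops dosing carries 2-working-day notice if it is unrelated, and also if it is related and either serious or unanticipated. If it is related, non-serious and anticipated, no deadline is stated. Item 4 concerns at most 16 planned participants, during Weeks 0 to 16.

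The mismatch between the two sections is plain on the text. Whether it leaves a working gap depends on how the site classifies a severe eye event, which the protocol text shown does not settle. Severe related events still go to the SMC under item 6, and no endpoint or analysis is affected.

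**What to change.** In section 13.1 item 4, remove the restriction of grade 3 or 4 eye events to unrelated ones and say that the notice applies regardless of causality. Alternatively, refer to section 6.1.7.2 item 3 in the way that item 5 refers to 6.1.7.2 for liver tests. The cross-reference has the advantage that the two rules cannot drift apart again.

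With either wording, every discontinuation under the eye rule carries the 2-working-day notice. The cost is a one-phrase amendment, with no added participants, visits or procedures. The change does not extend item 4 to eye events after the last planned infusion, which stay with the other reporting clauses.

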13.2 Monitoring

Safety monitoring will be conducted by the study investigators, by the external Study Monitoring Committee (SMC) and by the International AIDS Vaccine Initiative (IAVI). IAVI. The RUH-IRB will conduct the initial review of the proposed study and will follow progress through annual reports and by immediate notification of serious adverse events. External monitoring will occur at least quarterly, and will be conducted by IAVI.

13.3 Adverse Event Classification

Adverse events will be graded using the Toxicity Grading Scale for Healthy Adult and Adolescent Volunteers Enrolled in Preventive Vaccine Clinical Trials (HIV-uninfected).

The CTCAE v4.03 grading scale will be used for reporting and grading adverse events related to infusion reactions and cytokine release syndromes in all groups (**Appendix B**).

13.4 Reporting Adverse Events

All adverse events will be reported to the IRB and the SMC at least annually. Serious Adverse Events, (SAEs) will be reported to the IRB and the SMC, within two working days of identification of the SAE. SAEs will be reported directly to the FDA, per 21 CFR 312.

13.5 Reporting Unanticipated AEs

Unanticipated Adverse Events (UAEs) will be reported to the IRB and SMC. UAEs that are related and greater than moderate severity must be reported to the IRB and SMC, within two working days of identification of the UAE. UAEs will be reported to the FDA, per 21 CRF 312.

13.6 Clinical Laboratory Improvement Amendment/Clinical Laboratory Evaluation Program (CLIA/CLEP)

This study includes tests that are not CLIA/CLEP certified. The results of such tests will not be used in clinical decision-making or shared with participants or their health care providers.

14 Clinical Trial Registration

The proposed study involves testing of FDA regulated drugs or biologics and will be registered at www.ClinicalTrials.gov.

15 Bibliography

- Armbruster, C., G. M. Stiegler, B. A. Vcelar, W. Jager, U. Koller, R. Jilch, C. G. Ammann, M. Pruenster, H. Stoiber and H. W. Katinger (2004). "Passive immunization with the anti-HIV-1 human monoclonal antibody (hMAb) 4E10 and the hMAb combination 4E10/2F5/2G12." J Antimicrob Chemother 54(5): 915-920.
- Baeten, J. M., D. Donnell, P. Ndase, N. R. Mugo, J. D. Campbell, J. Wangisi, J. W. Tappero, E. A. Bukusi, C. R. Cohen, E. Katabira, A. Ronald, E. Tumwesigye, E. Were, K. H. Fife, J. Kiarie, C. Farquhar, G. John-Stewart, A. Kakia, J. Odoyo, A. Mucunguzi, E. Nakku-Joloba, R. Twesigye, K. Ngure, C. Apaka, H. Tamooh, F. Gabona, A. Mujugira, D. Panteleeff, K. K. Thomas, L. Kidoguchi, M. Krows, J. Revall, S. Morrison, H. Haugen, M. Emmanuel-Ogier, L. Ondrejcek, R. W. Coombs, L. Frenkel, C. Hendrix, N. N. Bumpus, D. Bangsberg, J. E. Haberer, W. S. Stevens, J. R. Lingappa and C. Celum (2012). "Antiretroviral prophylaxis for HIV prevention in heterosexual men and women." N. Engl. J. Med. 367(5): 399-410.
- Caskey, M., F. Klein, J. C. C. Lorenzi, M. S. Seaman, A. P. West Jr., N. Buckley, G. Kremer, L. Nogueira, M. Braunschweig, J. F. Scheid, J. A. Horwitz, I. Shimeliovich, S. Ben-Avraham, M. Witmer-Pack, M. Platten, C. Lehmann, L. A. Burke, T. Hawthorne, R. J. Gorelick, B. D. Walker, T. Keler, R. M. Gulick, G. Fatkenheuer, S. J. Schlesinger and M. C. Nussenzweig (2015). "Viraemia suppressed in HIV-1-infected humans by broadly neutralizing anitbody 3BNC117." Nature 522:487-489.
- Cohen, M. S. and L. R. Baden (2012). "Preexposure prophylaxis for HIV--where do we go from here?" N. Engl. J. Med. **367**(5): 459-461.
